### **Secondary Objectives:**

- 1.2. To determine the overall survival with ofatumumab in the upfront setting in elderly, unfit CLL patients.
- 1.3. To evaluate the complete response rate and time to progression after repeated doses of ofatumumab in elderly, unfit patients with CLL.
- 1.4. To determine the plasma levels of ofatumumab in elderly, unfit patients.
- 1.5. To evaluate predictive capability of miRNAs detection in plasma samples.

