### **miRNA plasma levels and profiling**

Selected miRNA plasma levels in CLL patients will be determined.

Genome-wide profiling study on plasma samples collected from all the patients before the start of the treatment and we will further perform follow-up studies at specific time points (month 3, 6, 9 and 12) will be conducted by quantitative RT-PCR (Rossi et al., Blood 116, 945-952 2010).

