### **10.0 Statistical design**

This is a phase II trial to assess the activity and tolerability of ofatumumab in elderly (age 65 or greater), unfit patients with previously untreated CLL.

Response will be assessed after month 3, month 6 and every 6 months thereafter using the 2008 NCI-WG criteria. Toxicity will be score using CTCAE v4.0. The first time point to evaluate efficacy and toxicity will be at completion of month 6 of treatment. Toxicity will be monitored during the entire treatment.

The primary endpoint of this study is OR (CR + PR) and a Simon's two-stage optimum design will be used for this study. A sample size of 34 is chosen to differentiate between a good response rate of 70% and a poor response rate of 40% with 95% power at a significance level of 0.05. The trial will stop early due to lack of efficacy if there are 6 or fewer patients with OR in the first 14 patients. Lack of efficacy will also occur if there are 18 or fewer responses in 34 patients. Secondary endpoints are progression-free survival (PFS) and CR rate. PFS is defined as time from start of therapy to death or progression of disease and it will be calculated using Kaplan Meier estimates. Responses will be assessed by Fisher's exact test with intention to treatment analysis by pre-treatment characteristics. Potential relationships between ofatumumab plasma concentrations and clinical outcomes (e.g. OR) will be explored using regression analyses.

For the correlative studies, we will assess the association between survival data and miRNA marker expression using proportional hazards models and estimate the distributions of time-to-event outcomes using the Kaplan and Meier method. We will then compare these distributions among treatment or cohort groups using the log-rank test. We will compare the proportions of complete responses between positively and negatively expressed miRNAs that are therapeutic markers in various trials. Fifty-eight samples (2-3 sequential samples from each patient) will be required to achieve 80% power at a 2-sided significance level of 0.05 and Bonferroni adjustment for testing 10 markers, assuming that 50%

patients are marker positive and that the response rates in the positively and negatively expressed markers are 75% and 25%, respectively.

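### The miRNA power statement needs 58 independent patients but counts 2-3 serial samples per patient; with at most 34 patients, power is about 46%, not 80%

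*Combined protocol and SAP*

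**What the plan says.** Secondary objective 1.5 reads: "To evaluate predictive capability of miRNAs detection in plasma samples". The analysis is in the last paragraph of Section 10.0: "We will compare the proportions of complete responses between positively and negatively expressed miRNAs". The size statement follows: "Fifty-eight samples (2-3 sequential samples from each patient) will be required to achieve 80% power at a 2-sided significance level of 0.05", with a Bonferroni adjustment for 10 markers, half of patients assumed marker positive, and response rates of 75% and 25% in the two marker groups.

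The number of patients is set earlier in the same section: "A sample size of 34 is chosen to differentiate between a good response rate of 70% and a poor response rate of 40" per cent. There is an interim rule: "The trial will stop early due to lack of efficacy if there are 6 or fewer patients with OR in the first 14 patients".

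Section 9.0, whose title marks the correlative studies as optional, describes the sampling: "Genome-wide profiling study on plasma samples collected from all the patients before the start of the treatment", then "follow-up studies at specific time points (month 3, 6, 9 and 12". That is five time points per patient.

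The documents give no within-patient correlation, no repeated-measures method for the miRNA data, and no test specific to this comparison. Fisher's exact test is named only for response by pre-treatment characteristics. The paragraph mentions markers in various trials but names no other trial and no number of patients from one.

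**The concern.** The power statement counts samples, while its assumptions concern patients: half of patients are marker positive, and response belongs to the patient. If 58 is a requirement for independent patients, a second or third sample from the same patient does not count towards it. The trial cannot reach 58 patients, because its maximum is 34.

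The counts also fit poorly together. At 2-3 samples each, 58 samples come from only 20 to 29 patients (58/3 = 19.3; 58/2 = 29), while Section 9.0 plans five samples from each patient.

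At stake is how objective 1.5 is interpreted. A marker comparison said to have 80% power, with multiplicity control, invites the reader to take a null result as evidence that the marker does not predict response. The statement also leaves open whether the analyst may treat samples as the unit.

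**Working it through.** **Inputs, all from Section 10.0.** p1 = 0.75, p2 = 0.25; equal marker groups (50% positive); power 80%; two-sided 0.05 with Bonferroni for 10 markers, so 0.05/10 = 0.005 per marker; maximum 34 patients, or 14 after a stage 1 stop.

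**Step 1: reproduce 58.** With d = 0.50, mean proportion 0.50, z(0.9975) = 2.807 and z(0.80) = 0.842, the two-proportion formula per group is

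n = [z(0.9975)·√(2 × 0.5 × 0.5) + z(0.80)·√(0.75 × 0.25 + 0.25 × 0.75)]² / d²
= [2.807 × 0.7071 + 0.842 × 0.6124]² / 0.25 = 25.005.

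The continuity correction gives

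n' = (n/4)·[1 + √(1 + 4/(n·d))]² = (25.005/4)·[1 + √(1 + 4/12.50)]² = 28.87, so 29 per group and 58 in total.

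This matches the plan exactly. Other variants do not: 52 without the correction, 38 at 0.05 without Bonferroni (with the correction), 52 for one-sided 0.005 (with the correction). Full enumeration of Fisher's exact test at 29/29 gives 82.0% power (28/28 gives 78.4%). The formula has no term for within-patient correlation, so its 58 are independent units with one response each.

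**Step 2: power with the patients available.** For n per group:

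- Uncorrected normal: Φ{[d − 2.807·√(0.5/n)] / √(0.375/n)}. At n = 17: Φ{(0.5 − 0.4814)/0.1485} = 55.0%.
- Corrected normal: subtract a further 1/n in the numerator. At n = 17: Φ{(0.5 − 0.0588 − 0.4814)/0.1485} = 39.3%.
- Fisher: sum the binomial probabilities of all tables with two-sided p ≤ 0.005.

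| Patients (split) | Fisher | Corrected normal | Uncorrected normal |
|---|---|---|---|
| 58 (29/29) | 82.0% | 80.3% | 87.6% |
| 34 (17/17) | 46.5% | 39.3% | 55.0% |
| 29 (14/15) | 38.8% | 28.7% | 44.7% |
| 20 (10/10) | 11.9% | 12.0% | 25.5% |
| 14 (7/7) | 10.1% | 4.5% | 14.0% |

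Marker status will not split evenly by design. Averaged over random 50% splits, Fisher power is 48.1% with 34 patients, 36.5% with 29, 18.4% with 20 and 9.3% with 14. An even split is not a ceiling (15/19 gives 51.7%), but nothing here approaches 80%.

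**Step 3: detectable difference.** At 17/17, with rates symmetric about 50%, Fisher power is 77.7% for a 62-point difference, 79.9% for 63 points (81.5% vs 18.5%) and 82.0% for 64 points. About 63 points is needed, against the 50 points assumed.

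**Step 4: a conditional risk.** The plan does not say outright that serial samples would be pooled as independent. If they were, the per-marker false-positive rate could exceed the intended 0.5%. In a null simulation (58 samples, one response per patient, Fisher p < 0.005) it ranged from 0.2% to 4.6% over 27 assumed scenarios: response rate 10-50%, within-patient marker correlation 0.2-0.8, 20 to 34 patients. It exceeded 0.5% in 19 of them. These settings are assumptions, and the main point does not depend on them.

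**The case against.** **Serial samples may carry information.** Response is assessed at months 3 and 6 and every 6 months after, so samples could be paired with same-time responses. With 34 patients, 2-3 samples each gives 68 to 102 samples. If the design effect is 1 + (m − 1) × marker correlation × response correlation, the effective number is about 54 to 68 when both correlations are 0.5 and 41 to 45 when both are 0.8. Some scenarios therefore reach 58. This stands as a possibility, but it needs assumed correlations, more samples than the plan states, and a repeated-measures analysis that the plan does not contain. With the plan's own 58 samples, an assumed overall within-patient correlation of 0.3 to 0.8 gives uncorrected-normal power of about 73% to 51% at two samples per patient and 59% to 30% at three.

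**The sentence may mean 58 patients with 2-3 samples each.** The fault is then one of feasibility instead of pseudo-replication. The shortfall is the same, because 34 is the cap.

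**The paragraph may be programme text covering several trials.** It refers to various trials and to comparing treatment or cohort groups, in a single-arm study. No other source of patients is named, so this cannot support the figure; the sponsor can say if it was meant.

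**The 46% inherits a weak assumption.** Rates of 75% and 25% at 50% prevalence imply an overall complete response rate of 50%, which the documents do not support. This is fair. With an assumed 50% vs 10%, Fisher power at 17/17 is 27%. The 46% is power on the plan's own assumptions, not a forecast.

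**Five planned samples need not conflict with using 2-3.** This is also fair; the mismatch is a matter of clarity only.

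**The study is optional and the remedy is only wording.** That limits the consequences, but the comparison serves a listed secondary objective and carries a formal power claim.

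**Conclusion.** The concern holds. The arithmetic behind 58 is right, but it counts independent patients. On the plan's own assumptions, all 34 patients give about 46% power by Fisher's exact test at an even split (39% to 55% across standard methods) against the stated 80%, and less if fewer patients take part or the trial stops at 14. This rests on one marker value and one response per patient, 75% vs 25%, and a two-sided level of 0.005 per marker. It should be fixed, because the stated power of a secondary objective is one the design does not have. The two-stage design and the primary endpoint are untouched.

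**What to change.** In Section 10.0, make the patient the unit of the marker-response comparison, use the pre-treatment sample already planned for every patient, and keep complete response as the outcome. Replace the 58-sample sentence with, for example:

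> With 34 patients (17 marker positive, 17 negative), power is about 46% by Fisher's exact test (39-55% across standard methods) for 75% vs 25% at two-sided alpha 0.005; 80% power requires a difference of about 63 points. This comparison is exploratory.

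Add that these figures are conditional on the assumed rates, which imply 50% complete response overall, and that the 63 points applies to rates symmetric about 50%. If serial samples are to be analysed, specify a model that clusters on patient (GEE or mixed model). If patients from other trials are meant to contribute, name the source and the number.

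The cost is wording in Section 10.0 and a less favourable stated power. No patients, samples or endpoints are added.

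### The 58-sample miRNA response comparison can only be filled with samples from month 3 onward, so a marker that merely tracks clearing disease could be called predictive

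*Combined protocol and SAP*

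**What the plan says.** Secondary objective 1.5 (Section 2.0) is "To evaluate predictive capability of miRNAs detection in plasma samples".

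The miRNA part of Section 9.0 describes "plasma samples collected from all the patients before the start of the treatment", then "follow-up studies at specific time points (month 3, 6, 9 and 12". No sample is scheduled between baseline and month 3.

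Section 10.0 compares complete response (CR) proportions between marker-positive and marker-negative groups. Its sample-size statement is "Fifty-eight samples (2-3 sequential samples from each patient) will be required to achieve 80% power", at a two-sided 0.05 level with Bonferroni adjustment for 10 markers, 50% marker positive, and response rates of 75% and 25%. For survival the text is "we will assess the association between survival data and miRNA marker expression using proportional hazards models", without saying which sample supplies the expression value.

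On timing, Section 10.0 says "Response will be assessed after month 3, month 6 and every 6 months thereafter", and also "The first time point to evaluate efficacy and toxicity will be at completion of month 6 of treatment". The maximum enrolment is 34.

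**The concern.** A marker is useful for prediction if its level is known before the outcome begins to unfold. A plasma level at month 3, 6, 9 or 12 is measured under treatment, when the leukaemic burden may already have fallen. If a miRNA changes as cells clear, its level at that time is partly a consequence of response. A test that mixes such samples with baseline samples can then find an association for a marker that carried no information before treatment.

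At stake is the conclusion on objective 1.5: the trial could put forward a false predictive marker. This differs from the fault of counting several samples from one patient as independent. A mixed model, or a single month 6 sample per patient, would remove the dependence and leave the timing fault in place.

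**Working it through.** **1. Reproduce the 58.** Inputs, all from Section 10.0: p1 = 0.75, p2 = 0.25, power 80%, equal groups, per-marker two-sided alpha = 0.05/10 = 0.005. So z = 2.807 for alpha, z = 0.842 for power, and mean proportion 0.5.

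- Uncorrected n per group = [2.807 × √(2 × 0.5 × 0.5) + 0.842 × √(0.75 × 0.25 + 0.25 × 0.75)]² / 0.5² = 25.0.
- With continuity correction: (25.0/4) × [1 + √(1 + 4/(25.0 × 0.5))]² = 28.9, so 29 per group and 58 in total.

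This matches the plan exactly. Rounding up without the correction gives 52; unadjusted alpha gives 30, or 38 with the correction. The 58 is therefore 29 + 29 independent units, and the plan fills them with sequential samples.

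**2. Count the on-treatment samples.** There is one pre-treatment sample per patient.

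- All 34 patients contribute a baseline sample: 58 − 34 = 24 on-treatment (41%). This is the minimum.
- Two samples per patient: 58/2 = 29 patients, so 29 on-treatment (50%).
- Three samples per patient: 58/3 = 19.3 patients, so about 39 on-treatment (67%).

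**3. Illustrate the effect.** The documents give no figure for how far a miRNA moves with response, so these are assumptions: marker unrelated to response at baseline; correlation 0.5 between baseline and on-treatment level; on-treatment level shifted in responders by 0.5, 1.0 or 1.5 SD; split at the median (matching the plan's 50% positive); all samples pooled; Fisher's exact test at 0.005. The 50% response rate is the plan's implied average, (75% + 25%)/2. The 20% rate is a further assumption, because no expected CR rate is stated.

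| Layout | Responders | No shift | 0.5 SD | 1.0 SD | 1.5 SD |
|---|---|---|---|---|---|
| 29 patients × 2 | 50% | 1% | 2% | 8% | 16% |
| 19 patients × 3 | 50% | 2% | 5% | 17% | 36% |
| 29 patients × 2 | 20% | – | 1% | 3% | 4% |
| 19 patients × 3 | 20% | – | 3% | 7% | 14% |

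With one baseline sample per patient and 50% responders, the same marker is declared in about 0.2% of trials. The no-shift column shows the part due to repeated samples alone. Repeat runs differ by a few percentage points at most (36% to 40% in the largest cell).

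**4. Power with baseline samples only.** With 34 patients split 17 v 17 and 75% v 25% at alpha 0.005:

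- Normal approximation: Φ{[0.5 × √17 − 2.807 × √0.5] / √0.375} = Φ(0.125) = 55%.
- Exact Fisher: 46%.

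For comparison, exact Fisher at 29 v 29 gives 82%.

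**The case against.** The strongest reply is that the plan states how many samples are required but not how sequential samples enter the test. Its prevalence assumption is worded for patients, so classifying each patient by the baseline sample, or by change, is not excluded. That is true, but it does not rescue the 58: baseline samples alone cannot exceed 34, and no sentence restricts the miRNA comparison to them. The reference in Section 10.0 to pre-treatment characteristics belongs to the general response analysis and is not carried into the correlative paragraph.

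Second, the outcome is CR, which may be called after month 3, and the plan names completion of month 6 as its first efficacy time point. Some month 3 samples may precede the CR call, and an early on-treatment level that precedes a later outcome can have its own use. This stands. A reader might infer that response is already known whenever a later sample is drawn; the documents do not support that for CR at month 3. Such a sample still follows about three months of treatment and is not a pre-treatment predictor.

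Third, a reader might infer that the survival models contain immortal-time bias. They would if a month 3–12 level were entered as a fixed covariate with time counted from start of therapy. The plan does not say this, and it defines that time origin only for PFS. What can be said is that the sample is unspecified.

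Fourth, larger error rates can be produced: one on-treatment sample in each of 34 patients gives about 18% and 54% at 1.0 and 1.5 SD. The plan does not describe that layout, so the pooled figures are the relevant ones.

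Finally, the work is an optional correlative study. It does not touch the overall response endpoint or the two-stage stopping rule.

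**Conclusion.** The point holds as a gap in specification with a real consequence. The plan's own count forces at least 24 of 58 samples to come from month 3 or later, and nothing keeps them out of the test for objective 1.5. A marker that only tracks response could therefore be called predictive. To say that it would be goes too far, because the chance depends on how strongly the marker moves with response.

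Under the assumed shifts the false-positive chance per marker runs from about 2% to 36% at 50% responders and about 1% to 14% at 20%, part of it (1% to 2% at 50% responders) from repeated samples. The sample counts rest only on the documents; the percentages rest on the assumed correlation, shifts and pooling. The effect is confined to a secondary objective, so this should be corrected but does not threaten the primary analysis.

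**What to change.** In Section 10.0:

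- State that the CR comparison and the proportional hazards models for objective 1.5 use one pre-treatment sample per patient.
- Replace the 58-sample, 80% power statement with the achievable power: about 46% by exact Fisher (about 55% by normal approximation) with 34 patients split 17 v 17, under the plan's own rates and Bonferroni level.
- Analyse the month 3–12 samples separately, as change over time or monitoring. If they are related to survival, use a landmark analysis (patients still at risk at the sample date, time counted from that date) or a time-dependent covariate, and do not report the result as pre-treatment prediction.

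The cost is a few sentences and no new samples. The downside is that the predictive test rests on one sample per patient and the stated power falls. That shortfall already exists, since 58 independent patients were never available; the change makes it visible.

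### Bonferroni over ten miRNA markers is valid but, if Fisher's exact test is used, spends only about 2-3% of the 5%; a permutation step-down would recover a modest, conditional amount of power

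*Combined protocol and SAP*

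**What the plan says.** Section 10.0 (Statistical design) plans this marker analysis: "We will compare the proportions of complete responses between positively and negatively expressed miRNAs that are therapeutic markers in various trials". Its size is given as "Fifty-eight samples (2-3 sequential samples from each patient) will be required", for "80% power at a 2-sided significance level of 0.05 and Bonferroni adjustment for testing 10 markers". The assumptions are that half the patients are marker positive and that "response rates in the positively and negatively expressed markers are 75% and 25%, respectively".

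The trial enrols at most 34 patients. The one test that Section 10.0 names for response comes in the preceding paragraph and concerns clinical covariates: "Responses will be assessed by Fisher's exact test with intention to treatment analysis by pre-treatment characteristics". No test is named for the marker comparison. The documents also give no cut-point for marker positivity, no correlation between markers, and no step-down or resampling method. Section 9.0 places the miRNA work under optional correlative studies, with sampling before treatment and at months 3, 6, 9 and 12.

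**The concern.** Bonferroni guarantees that the family-wise error is at most 5%; it does not use all of it. In a small sample with an exact test, each marker's true size can be well below 0.005, because only a few p-values are attainable. The unused error is lost power. In 34 patients the marker comparison is already short of power and the design offers no more patients, so a correction that holds the same 5% and uses more of it is worth considering. At stake is the chance of detecting a real marker. The risk of a false claim is not at issue, because it is controlled under either method.

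**Working it through.** **Inputs (all Section 10.0).** Two-sided 0.05 over 10 markers, so 0.05/10 = 0.005 each; 80% power; 75% v 25%; 50% positive; 58 samples; at most 34 patients.

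**Step 1: reproduce the 58.** With z(0.9975) = 2.807 and z(0.80) = 0.842:

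n0 = [2.807·√(2·0.5·0.5) + 0.842·√(0.75·0.25 + 0.25·0.75)]² / 0.5² = 25.005, so 26 per group, 52 in total.

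With continuity correction: n = (n0/4)·[1 + √(1 + 4/(n0·0.5))]² = 28.87, so 29 per group, **58 in total**.

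Exact enumeration of Fisher's test gives 82.0% power at 29+29 and 78.4% at 28+28. The 58 therefore fits a Fisher-type test and not the uncorrected formula.

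**Step 2: error spent by Bonferroni with Fisher, 34 patients, 50% response overall.** Family-wise error for ten independent markers is 1 − (1 − size)^10.

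| Layout | Size per test | Family-wise error |
|---|---|---|
| Exact 17/17 split | 0.00228 | 2.3% |
| Positive count varies around 50% | 0.00276 | 2.7% |
| Ideal continuous test | 0.00500 | 4.9% |

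The last row shows the cause: Bonferroni alone would spend 4.9%, and the rest of the shortfall is discreteness. For 17 v 17 with 17 responders in total, 13 v 4 gives p = 0.0053 and fails; the next table, 14 v 3, gives p = 0.0004. With other responder totals some tables fall just under the limit (12 v 3: 0.0049; 11 v 2: 0.0039). Correlation matters less: simulated family-wise error was 2.7%, 2.6%, 2.8% and 2.3% at correlations 0, 0.3, 0.6 and 0.8. At lower overall response rates less is spent: 1.0-2.1% at 25%, and 0.3% or less at 10%.

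**Step 3: why step-down min-P cannot do worse.** For the smallest observed p, the exact adjusted value is P(min p_j ≤ p) ≤ Σ P(p_j ≤ p) ≤ 10p, which is the Bonferroni value. The second inequality is strict when markers have different positive counts, because then some cannot attain p exactly. If all ten have the same split, each term equals p, and only overlap between markers can help.

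**Step 4: simulated power for one true marker among 10, 75% v 25%** (34 patients, 2,500 trials, 999 permutations; simulation error about 1 point on power).

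| Layout | Correlation | Power: Bonferroni | Power: min-P | Family-wise error: Bonferroni, min-P |
|---|---|---|---|---|
| Counts vary | 0 | 49.5% | 55.7% | 2.7%, 4.2% |
| Counts vary | 0.5 | 49.3% | 56.0% | 2.2%, 4.4% |
| Counts vary | 0.8 | 47.1% | 57.2% | 2.1%, 4.2% |
| Median split | 0 | 47.6% | 46.2% | 2.4%, 2.2% |
| Median split | 0.5 | 45.6% | 47.7% | 2.2%, 2.2% |
| Median split | 0.8 | 46.2% | 51.0% | 2.1%, 2.4% |

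By Step 3, the apparent loss of 1.4 points in the fourth row is Monte Carlo error. Other runs with varying counts in 34 patients gave gains from about 5 points (46.8% to 52.2%) to about 11 (47.9% to 58.5%).

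With 29 patients (58/2) the gains were 6-12 points with varying counts and about 1-6 with a median split. With 20 (58/3 = 19.3, rounded up), Bonferroni power was 11-19% and min-P power 16-28% over both layouts.

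**Step 5: sensitivity to the test.** With an uncorrected chi-square test in 34 patients, Bonferroni spends 3.6-4.7%, and the difference in power from min-P was about −2 to +4 points. Holm in place of Bonferroni added 0-1 point.

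**The case against.** The strongest objection is that nothing here is wrong. Bonferroni is prespecified, valid and simple, the analysis is an optional correlative, and power stays far below 80% whichever correction is used. That stands, and it sets the priority.

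Several stronger readings are tempting, but the documents do not support them:

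- **A general gain of 5-12 points.** A reader might infer this from the unspent error. It needs positive counts that differ between markers. The plan assumes 50% positive and gives no cut-point; a median split is one natural reading, and there the gain is about 0-5 points in 34 patients with family-wise error still near 2%.
- **Fisher's test as the plan's stated marker test.** It is named for pre-treatment characteristics only. Its use for the markers is an inference from the 58.
- **Discreteness and marker correlation as two losses that add up.** The family-wise error is nearly flat up to correlation 0.6, and the documents give no marker correlations.
- **The same change for the survival comparisons.** Section 10.0 does not state ten survival tests or a Bonferroni correction for them, and log-rank and proportional hazards tests do not have the coarseness shown here. No calculation supports that extension.

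**Conclusion.** The point holds as an optional, low-priority improvement. If Fisher's exact test is used in at most 34 patients, Bonferroni over ten markers spends about 2-3% of the 5% at the plan's rates, mainly through discreteness. Step-down min-P keeps the 5% guarantee and adds about 5-12 points of power when positive counts vary, or about 0-5 when every marker is split at its median. The test, the cut-point and marker correlations of 0 to 0.8 are assumptions, because the documents state none of them.

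A reader might infer that the change repairs the marker analysis. It does not: power in 34 patients is about 46-59% across both methods, against the stated 80%. The larger problem is separate: 58 serial samples, at 2-3 per patient, come from about 19-29 patients and cannot count as 58 independent observations.

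**What to change.** In Section 10.0, replace the Bonferroni clause for the marker v complete-response comparisons with wording such as: *Each of the 10 pre-named markers will be compared with complete response by Fisher's exact test, using one pre-treatment record per patient. Family-wise error will be controlled at two-sided 5% by the Westfall-Young step-down min-P procedure, permuting response status across patients, with at least 10,000 permutations and a fixed seed.* State the rule that defines marker positivity in the same edit, because the gain depends on it. Leave the survival comparisons as they are.

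The cost is SAP wording and a few lines of code, with no new data or patients. The downside is that adjusted p-values come from a seeded permutation run, and simultaneous confidence intervals are less simple than Bonferroni ones. If the sponsor prefers no permutation, Holm is valid and never less powerful than Bonferroni, but it brings almost nothing here.
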